### 9.10.28. Virus Serology

Blood samples will be collected for testing for hepatitis B and hepatitis C as indicated in Table 5. If the initial hepatitis C result is positive, then the patient will need to return for an unscheduled hepatitis C virus ribonucleic acid (HCV RNA) assessment to determine if the virus is present at the current time. If the results of this test are negative, the patient may continue in the Screening process.

### 9.10.29. Pharmacokinetic (PK) Blood Samples

Blood samples for determination of plasma bardoxolone methyl and potential metabolite concentrations will be drawn as indicated in Table 5. Patients must be instructed to not take their study drug prior to coming to the clinic for visits when PK samples will be collected. Patients will be asked by site personnel to provide the time of their last two administrations of study drug prior to the blood samples being collected. Blood sample collection instructions should be referenced in the laboratory manual. Patients must administer the study drug dose in the clinic on PK sample collection visits after the 0 hour PK blood sample is collected. Patients will have blood samples for PK analysis drawn just prior to (0 hour) and after (2 and 4 hours) dose administration.

The date and time of collection of all PK blood samples should be recorded; however, any deviations from the protocol-specified sampling times will not be considered protocol deviations.

Sample time deviations will be summarized in the study report. Dates in the case report form should be recorded in an unambiguous format (e.g., DD MMM YYYY) and time should be recorded to the nearest minute (e.g., HH:MM using the 24-hour clock). Blood samples not drawn should be recorded as such.

### 10. STUDY DRUG MATERIALS AND MANAGEMENT

# 10.1. Study Drug

Bardoxolone methyl capsules, 5 mg and 15 mg, will be used in this study.

# 10.2. Study Drug Packaging and Labeling

The study drug will be supplied in tamper-evident kits containing two high-density polyethylene (HDPE) bottles. Each bottle will utilize foil induction-seal liners and a child-resistant closure. Each bottle of study drug will contain 30 capsules of 5 mg or 15 mg strength bardoxolone methyl or the matching placebo capsules. Each bottle will also contain a desiccant insert that must not be ingested. Labeling on each kit bottle will contain at minimum the following information:

- Medication ID number;
- Protocol 402-C-1702;
- Caution Statement: New Drug Limited by Federal Law to Investigational Use.
   Keep out of sight and reach of children;
- Control or lot number;
- Store at 20° 25°C (68° 77°F), short term excursions allowed to 15° 30°C (59° 86°F);
- Reata Pharmaceuticals, Inc., Irving, TX.

A double-panel label will be presented on the treatment kit carton containing this and other information as well.

# 10.3. Study Drug Storage

The stability of the drug product has been and is currently being evaluated in ongoing studies.

Investigative sites must store the investigational product in a secure location with room temperature conditions of  $20^{\circ}$  -  $25^{\circ}$ C ( $68^{\circ}$  -  $77^{\circ}$ F), with short term excursions allowed to  $15^{\circ}$  -  $30^{\circ}$ C ( $59^{\circ}$  -  $86^{\circ}$ F).

# 10.4. Study Drug Administration

Please refer to Section 9.10.13 for details on study drug administration. Clear instructions will be provided to the patient regarding the number and type of capsules to be ingested at each study drug administration time point listed in Table 5. Patients must be instructed to continue taking study drug once daily up through their Week 12 visit unless: (1) the patient has been otherwise instructed by the investigator or (2) the patient has been formally discontinued from study treatment

# 10.5. Study Drug Accountability

The investigator, or designee, will maintain a record of all study drug received, dispensed, and returned to the Sponsors' designee. No study drug shall be destroyed by the clinical site unless directed in writing to do so by the Sponsor's quality assurance department. Study drug bottles and any unused capsules should be returned to the study staff for eventual disposition by the Sponsor. The number of capsules returned at each visit will be recorded for each bottle in the kit.

# 10.6. Study Drug Handling and Disposal

At the conclusion of the study or in an instance of planned study drug replacement, the Sponsor or its designee will direct the site regarding the final disposition of study drug.

### 11. SAFETY ASSESSMENTS

# 11.1. Safety Parameters

To avoid inter-observer variability, every effort should be made to ensure that the same individual who made the initial baseline determinations completes all safety assessments. Safety parameters include vital sign measurements, ECG results, AEs, SAEs, weight, and laboratory test results (clinical chemistry, hematology, urinalysis and microscopy).

# 11.2. Adverse and Serious Adverse Events

### 11.2.1. Definition of Adverse Events

### 11.2.1.1. Adverse Event

An AE is defined as any untoward medical occurrence in a patient regardless of its causal relationship to study drug. An AE can be any unfavorable and unintended sign (including any clinically significant abnormal laboratory test result), symptom, or disease temporally associated with the use of the study drug, whether or not it is considered to be study-drug related. Included in this definition are any newly-occurring events or previous condition that has increased in severity or frequency since the administration of study drug.

All AEs that are observed or reported by the patient during the study (from time of administration of the first dose at the Day 1 visit until the final visit indicated in Table 5 must be reported, regardless of their relationship to study drug or their clinical significance.

### 11.2.1.2. Serious Adverse Event

An SAE is any AE occurring at any dose and regardless of causality that:

- Results in death;
- Is life-threatening;
- Requires inpatient hospitalization or prolongation of existing hospitalization;
- Results in persistent or significant incapacity or substantial disruption of the ability to conduct normal life functions;
- Is a congenital anomaly or birth defect in an offspring of a patient taking study drug;
- Is an important medical event.

The term "life-threatening" refers to an event in which the patient was at immediate risk of death at the time of the event. It does not refer to an event that hypothetically might have caused death if it were more severe.

Important medical events are those that may not meet any of the criteria defined above; however, they may be considered serious when, based upon appropriate medical judgment, they may jeopardize the patient and may require medical or surgical intervention to prevent one of the other outcomes listed in the SAE definition.

Pregnancy is not considered an AE; however, information will be collected for any pregnancies that occur during the study (from the time of the first dose of study drug until the final visit indicated in Table 5 or until 30 days following administration of the final dose, as appropriate). Certain pregnancy outcomes will require submission as an SAE. (See Section 9.8).

The investigator is responsible for reporting to Reata or designee all AEs and SAEs that are observed or reported by the patient during the study (from the time of administration of the first dose of study drug until the final visit indicated in Table 5 or until 30 days following administration of the final dose, as appropriate), including events resulting from protocol-associated procedures as defined in relevant legislation, and regardless of their relationship to study drug or their clinical significance. The Sponsor may request additional information from the investigator to ensure the timely completion of accurate safety reports.

All SAEs reported or observed during the study must be followed to resolution or until the investigator deems the event to be chronic or the patient to be stable. Reata or designee may contact the investigator to obtain additional information on any SAE which has not resolved at the time the patient completes the study.

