- e Screening eligibility procedures do not need to be repeated on Day 1; however, a review of any changes in eligibility criteria should be evaluated prior to Day 1 procedures, and a urine pregnancy test should be performed for WOCBP.
- f An echocardiogram performed at the Screen A visit or within 6 months prior to Day 1 may be used to determine eligibility.
- g A serum pregnancy test will be performed at the Screen A visit for WOCBP or at any point in time if a pregnancy is suspected. All other pregnancy assessments will be urine pregnancy tests.
- h AE assessments on Day 1 should be performed following study drug administration.
- Only patients enrolling in the IgA nephropathy cohort or the FSGS cohort are required to have a kidney biopsy. Patients with definitive diagnosis of IgA nephropathy or FSGS from previous biopsy will not have a kidney biopsy as part of the study, but must provide diagnosis documentation from previous kidney biopsy for eligibility.
- j Only patients enrolling in the T1D cohort are required to have fasting C-peptide levels assessed. Patients should be instructed to fast prior to study visit.
- k Only patients enrolling in the ADPKD disease cohort are required to have genetic testing. Patients with confirmed PKD1 mutations from previous genetic testing will not have genetic testing performed as part of the study, but must provide documentation of genetic mutation for eligibility.
- Albumin to creatinine ratio will be measured by first morning void spot urine collection. Appropriate containers for the collection will be provided to the patient at the visit prior to collection.
- mPatients must be instructed to not take their study drug prior to coming to the clinic for visits when PK samples will be collected. Patients must administer the study drug dose in the clinic on PK sample collection visits after the 0 hour PK blood sample is collected. Patients will have blood samples for PK analysis drawn just prior to (0 hour) and after (2 and 4 hours) dose administration.

Abbreviations: EoT= end-of-treatment; ECG = electrocardiogram, F/U = follow-up; PK = pharmacokinetic, WOCBP = women of child-bearing potential

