#### 9.10.16. Adverse Event Collection

Patients will be observed for general appearance, presence of illness or injury, or signs indicative of a concurrent illness as indicated in Table 5. Patients must be instructed to volunteer any information regarding AEs on or after the first dose of study drug or query the patients with an open question regarding any AEs they may be experiencing (e.g., "How have you been feeling since your last visit?"). Any findings are to be documented. Patients must be asked if they have been hospitalized, had any accidents, used any new medications, or changed concomitant medication regimens (including prescription drugs, over-the-counter medications, vitamins, herbal products, and minerals). Responses must be documented in the source documents.

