### 9.10.17. Kidney Biopsy

Kidney biopsies will be performed as indicated in Table 5 for patients enrolling in the IgAN or FSGS cohorts to determine patient eligibility. Detailed instructions will be provided in a separate laboratory manual provided to the investigator.

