# 11.6. Recording Adverse Events

All conditions present prior to the administration of the first dose of study drug (Day 1) should be documented as medical history. After the first dose, documentation of AEs shall continue until 30 days (+/- 3 days) following administration of the final dose of study medication, regardless of the relationship of the AE to study drug. Information to be collected includes type of event, date of onset, date of resolution, investigator-specified assessment of severity and relationship to study drug, seriousness, as well as any action taken.

While an AE is ongoing, changes in the severity (e.g., worsening and improving) should be noted in the source documents, but when documenting the AE, only the total duration and greatest severity should be recorded in the eCRF. AEs characterized as intermittent require documentation of onset and duration.

All drug-related (possibly, probably, or definitely related, see Section 11.4) AEs and abnormal laboratory test results reported or observed during the study must be followed to resolution (either return to baseline or within normal limits). All other AEs will be followed through the final visit indicated in Table 5, as appropriate.

AEs resulting from concurrent illnesses, reactions to concurrent illnesses, reactions to concurrent medications, or progression of disease states must also be reported. Preexisting conditions (present before the start of the AE collection period) are considered concurrent medical conditions and should NOT be recorded as AEs. However, if the patient experiences a worsening or complication of such a concurrent condition, the worsening or complication should be recorded as an AE. Investigators should ensure that the AE term recorded captures the change in the condition (e.g., "worsening of..."). Any improvement in condition should be documented per Section 9.10.11.

Each AE should be recorded to represent a single diagnosis. Accompanying signs (including abnormal laboratory test values or ECG findings) or symptoms should NOT be recorded as additional AEs. If a diagnosis is unknown, sign(s) or symptom(s) should be recorded as an

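### AE and SAE collection opens at first dose, so a complication of the protocol's own screening kidney biopsy has no defined SAE report to the sponsor

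*Protocol*

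**What the plan says.** **The procedure.** Protocol Section 9.10.17 states: "Kidney biopsies will be performed as indicated in Table 5 for patients enrolling in the IgAN or FSGS cohorts to determine patient eligibility". Table 5 places the biopsy at Screen A. A footnote to the table exempts patients whose diagnosis is already documented by an earlier biopsy.

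**The collection window.**
- Section 11.2.1.1 dates AE reporting "from time of administration of the first dose at the Day 1 visit until the final visit indicated in Table 5".
- Section 11.2.1.2 dates the investigator's duty to report AEs and SAEs "from the time of administration of the first dose of study drug until the final visit indicated in Table 5". The same sentence then adds "including events resulting from protocol-associated procedures as defined in relevant legislation".
- Section 9.10.16: "Patients must be instructed to volunteer any information regarding AEs on or after the first dose of study drug".
- Table 5 has no AE collection at Screen A or Screen B, and its footnote says "AE assessments on Day 1 should be performed following study drug administration".

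**What happens to earlier events.** Section 11.6 says "All conditions present prior to the administration of the first dose of study drug (Day 1) should be documented as medical history", and also "Preexisting conditions (present before the start of the AE collection period) are considered concurrent medical conditions and should NOT be recorded as AEs". It makes an exception for a condition that later worsens or becomes complicated.

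**The SAP.** Section 8.1 limits the safety analysis set to patients who took study drug. Section 12.1.1 counts treatment-emergent events from the first dose and also plans a listing of every reported AE, treatment-emergent or not. Section 9.4 codes, summarises and lists medical history.

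**The concern.** A biopsy done to establish eligibility is an invasive procedure that some candidates undergo because of the trial. If one of them is admitted to hospital with a complication, the event meets a seriousness criterion in Section 11.2.1.2. On the dates given, though, no SAE form is called for.

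What is at stake is protection and oversight of participants, not the estimate of the drug's effect. The study may use up to 60 centers, and only the sponsor sees all of them. If one center has one complication and another center has a second, a pattern can be recognised only if both reach the sponsor by a defined route.

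**Working it through.** The point turns on dates and definitions, so the check is a comparison of passages. The only arithmetic concerns scale.

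**1. Order of events.** The biopsy is at Screen A (Table 5). The first AE assessment is on Day 1, after dosing (Table 5 and footnote). Section 8.3 allows up to 6 months of screening, so the interval without AE collection can be that long. This is a ceiling on screening, not the length of time a biopsy carries risk.

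**2. The procedure clause read in full.** In Section 11.2.1.2 the window and the procedure clause belong to one sentence. The clause widens the kinds of event that count; it does not move the start date. It therefore covers a blood draw at Week 4, for example, but not a biopsy at Screen A.

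**3. One complication followed along three paths.**
- *Resolved before Day 1, patient later dosed.* Section 11.6 makes it medical history at most. Table 5 schedules medical history only at Screen A, the same visit as the biopsy, so a complication arising afterwards has no scheduled point of entry. No SAE report is defined.
- *Still present at Day 1, then worse after dosing.* Section 11.6 makes the worsening an AE. The original event remains history.
- *Candidate fails screening.* There is no first dose, so the window never opens, and SAP Section 8.1 excludes the person from the safety analysis set. Acute kidney injury or acute dialysis during screening is itself an exclusion (Section 8.2), so a complication of that kind would send the candidate down this path.

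**4. A second instruction on the same events.** Section 9.10.11 asks that examination findings that are new or changed since Screening be reported as AEs if they meet the AE definition. Section 11.6 would call such a finding history if it preceded the first dose. SAP Section 12.6 sorts findings by onset date but does not say which of the two protocol rules sets the boundary.

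**5. Scale.** Section 7.2 plans about 25 patients per cohort, and two cohorts are concerned: 2 × 25 = 50. The documents do not give the share *p* who will need a study biopsy. The number of planned patients affected is *p* × 50:
- *p* = 0% gives 0;
- *p* = 10% gives 5;
- *p* = 50% gives 25;
- *p* = 100% gives 50.

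These shares are assumptions that span the possible range. Biopsied screen failures come on top, and their number is also unknown.

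**The case against.** Starting AE collection at first dose is a deliberate choice, and it suits the study of drug effects, because an event before dosing cannot be caused by the drug. Several further points can be made against the concern.

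- *A reader might infer that Section 11.2.1.2 contradicts itself.* It does not. The procedure clause is confined to the first-dose window, and it also defers to legislation that the documents do not reproduce and that may impose duties of its own.
- *A reader might infer that neither the sponsor nor the IRB/EC could learn of such harm.* The documents do not support that. Section 15.5 obliges the investigator to tell the IRB/EC about problems that put patients at risk, with no start date. Section 11.7 has investigators inform the IRB/EC of SAEs at their site, and its 24-hour rule names no start date either. Section 11.3 has patients questioned at every study visit, with answers kept in source records, and Section 13.1 has the sponsor's monitor review those records.
- *A reader might infer that the event is lost even in dosed patients.* It can appear as medical history, which SAP Section 9.4 lists.
- Many candidates may already have a diagnostic biopsy, so the number of study biopsies could be small or zero.

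All of this stands as a limit on the claim, but none of it closes the gap. The IRB/EC duties run site by site. Source records and monitoring might bring an event to light, but they set no form and no clock. The 24-hour rule in Section 11.7 applies to AEs, and the duty to report AEs is dated from first dose in Sections 11.2.1.1 and 11.2.1.2, so a site that files nothing has followed the protocol. Medical history does not carry the event as an SAE and offers nothing for a screen failure.

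**Conclusion.** The concern holds as a gap in reporting, not as a contradiction. For IgAN and FSGS candidates who need a study biopsy, a serious complication between Screen A and Day 1 has no defined SAE report and no 24-hour notice to the sponsor. If the candidate is never dosed, it has no place in the safety data. The partial routes make it possible that the sponsor hears of such an event, but they do not assure detection across centers.

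The size is 0 to about 50 planned patients plus an unknown number of biopsied screen failures. This takes the planned 25 per cohort as patients who go on to treatment. The documents give no complication rate, so no count of missed events can be derived. The primary endpoint, the safety set and the treatment-emergent tables are unaffected. This is an inexpensive improvement to participant protection; it does not threaten the trial's conclusions.

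**What to change.** **Protocol.** In Sections 9.10.16, 11.2.1.1, 11.2.1.2 and 11.6 and in Table 5:
- collect all SAEs, and any AE judged related to a procedure the protocol requires, from signed consent to first dose, with screen failures included;
- report those SAEs within 24 hours under Section 11.7;
- keep first dose as the start for all other AEs;
- reconcile Section 9.10.11 with Section 11.6, so that a finding between Screening and Day 1 has one stated destination.

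**SAP.** The Section 12.1.1 listing of all reported AEs can carry these events. Section 12 ties safety analyses to dosed patients, while Section 7 sends measurements from patients outside the analysis sets to the listings. One sentence should therefore state that consented patients who were never dosed are included. The treatment-emergent definition and tables stay as they are.

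**Cost.** A few additional SAE reports, plus changes to the protocol and the case report form guideline. No visit or procedure is added.

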# 11.3. Eliciting Adverse Event Information

At every study visit, patients must be asked a standard, non-directed question, such as, "How have you been feeling since your last visit?" to elicit any medically related changes in their well-being. They may also be asked if they have been hospitalized, had any accidents, used any new medications, or changed concomitant medication regimens (including prescription drugs, over-the-counter medications, vitamins, herbal products, and minerals). Responses must be documented in the source documents.

In addition to patient observations, AEs must be documented for any clinically significant diagnosis resulting from abnormal laboratory test values, physical examination findings, or ECG abnormalities, or from other documents that are relevant to patient safety.

# 11.4. Assessment of Causality

The investigator must use the following classifications and criteria to characterize the relationship or association of the study drug in causing or contributing to the AE:

Not Related: This relationship suggests that there is no association between the study drug and the reported event.

Unlikely Related: This relationship suggests that the temporal sequence of the event with study drug administration makes a causal relationship improbable and/or other factors also provide plausible explanations.

Possibly Related: This relationship suggests that treatment with the study drug caused or contributed to the AE. That is, the event follows a reasonable temporal sequence from the time of study drug administration, and/or, follows a known response pattern to the study drug, but could have been produced by other factors.

Probably Related: This relationship suggests that a reasonable temporal sequence of the event with study drug administration exists and, based upon the known pharmacological action of the drug, known or previously reported adverse reactions to the drug or class of drugs, or judgment

based on the investigator's clinical experience, the association of the event with study drug administration seems likely.

Definitely Related: This relationship suggests that a definite causal relationship exists between the drug administration and the AE, and other conditions (e.g., concurrent illness, progression/expression of disease state, or concurrent medication reaction) do not appear to explain the event.

